11.1.3 Treatment allocation

Patients will be randomised between SOC and SBRT + SOC in a 1:1 ratio. Patients will be randomised at different stages of their disease depending on the primary tumour site and in accordance with the inclusion and exclusion criteria. Treatment allocation will use minimisation with balancing factors of primary tumour site (breast, NSCLC, prostate) and centre. In tumour sites where there is felt to be a further important prognostic variable which may affect the primary PFS endpoint, a further stratification will be performed, as outlined below, to ensure the 2 treatment groups are balanced.

- **Breast:** patients will be stratified additionally into ER+ (relapsed post adjuvant therapy) vs all other subgroups, to reflect the difference in median PFS. It is acknowledged that breast cancer is a heterogeneous disease, essentially composed of several sub-groups with varying prognosis, dependent on receptor status, disease free interval (DFI) and prior adjuvant therapy. Whilst there is an argument in terms of homogeneity for limiting the eligible patient population to 1 sub-group only, such as ER+ disease, we feel it is more pragmatic at this stage to include all comers. The likely frequency of eligible patients within each sub-group is largely unknown and to ensure feasibility of recruitment, restricting trial entry to a particular sub-group from the outset is not warranted.
- **NSCLC:** stratified additionally into EGFR+ versus the remainder (with a similar rationale to the breast group).
- **Prostate:** patients will be stratified additionally into 2 groups:
 - 1) Patients who are endocrine therapy naïve
 - 2) Patients who are castrate resistant.

11.2 Endpoint definitions

11.2.1 Primary endpoint

Progression free survival is defined as time from randomisation to evidence of progression of cancer at any site or death from any cause.

Progression events should be imaging defined in all tumour types according to RECIST criteria. In addition, for prostate cancer patients progression by bone scan and PSA progression will be considered. On the rare occasions that progression cannot be measured by scan or biochemical failure (prostate only), clinical evidence of widespread progression will count as a PFS event.

Where SBRT specific consensus response assessment criteria exist for specific sites (e.g. spine), progression of SBRT treated lesions will be defined according to these guidelines.

11.2.2 Secondary endpoints

Recruitment rate is defined as the proportion of patients recruited to the trial. The denominator is the total number of patients required (i.e. 206 patients).

SBRT delivery is based on the proportion of patients allocated SBRT who received SBRT in the absence of new developing widespread disease and within the dosimetric constraints outlined in the SBRT protocol. The denominator is the number of patients allocated SBRT.

Overall survival is defined as time from randomisation until the time of death from any cause

Local lesion control is defined as time from randomisation until radiological evidence of progression at the treated site.

Clinician reported acute and late radiation related toxicity will be graded using NCI CTCAE v4.0/RTOG systems. Acute events are defined as those occurring up to 3 months follow up; late events are reported from 6 months post randomisation.

Patient reported quality of life will be measured using the EORTC QLQ C30 and EQ5D.

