3 TRIAL DESIGN

CORE is a phase II/III, multi-centre, non-blinded, parallel group randomised controlled trial in patients with breast, prostate or NSCLC primary cancer comparing standard of care (SOC) with or without SBRT for extra-cranial metastases. The aim of the phase II study is to demonstrate 1) feasibility of recruitment, 2) deliverability of the study in a multi-centre setting and 3) activity of SBRT, based on progression free survival, across the three tumour types. If all three aims are achieved the trial will be amended to roll into parallel tumour-site specific phase III trials.

Eligible patients are those with either primary breast, prostate or NSCLC who have presented with ≤ 3 extra-cranial, metachronous, oligometastases, all suitable for SBRT. Patients will be randomised in a 1:1 ratio to either SOC or SOC with the addition of SBRT. Choice of SOC treatment is at the discretion of the local oncologist and defined per patient prior to randomisation (see Section 9 Trial Treatment). Patients randomised to SBRT+SOC will receive a dose and fractionation regimen dependent on the metastatic site and proximity to dose limiting organs and normal tissues. Treatment will take place within 6 weeks of randomisation. The average scheme would be 3 treatments over 5 days but the maximum period of SBRT duration could be 8 treatments over 19 days.

All patients will be reviewed every 3 months with a clinical examination and tumour markers (where applicable) during years 1 and 2, and 6 monthly thereafter to 5 years. Staging and follow up imaging protocols will be tumour type dependent:

- **Breast:** 3 monthly CT scans for years 1 and 2, and 6 monthly thereafter to 5 years.
- **NSCLC:** 3 monthly CT scans for years 1 and 2, 6 monthly to year 3, then annually to 5 years.
- **Prostate:** CT scans will be performed at 6, 12 and 24 months with imaging triggered by appropriate PSA rises. A rising PSA defined as 2 successive PSA rises from nadir, measured a minimum of 4 weeks apart, will be used to trigger additional imaging (CT) between these time points.

All patients will have a toxicity assessment at each clinic visit and patient reported quality of life (QOL) assessment at 3, 6, 12, 18 and 24 months.

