4.2 Secondary endpoints

1. Recruitment rate and proportion of patients receiving SBRT (if allocated) in the absence of new developing widespread disease.
2. Recruitment of patients receiving SBRT within the dosimetric constraints.
3. Overall survival (OS).
4. Local lesion control.
5. Clinician reported acute and late radiation related toxicity (CTCAE version 4 and RTOG).
6. Patient reported QoL (EORTC QLQ C30 and EQ-5D questionnaire).

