11 STATISTICAL CONSIDERATIONS

11.1 Statistical design and sample size justification

11.1.1 Statistical design

CORE is a phase II/III, multi-centre, non-blinded, parallel group randomised controlled trial in patients with breast, prostate or NSCLC primary cancer. A randomised trial is the most appropriate design to address the research question and minimise potential sources of bias. Three tumour types are included in the trial as there is currently insufficient evidence to choose a single tumour site to investigate. Whilst the increased heterogeneity with this approach is acknowledged it was felt that this is the most pragmatic design for phase II. The decision to include NSCLC, breast and prostate cancer was made following wide consultation with clinicians across the UK, including the relevant Clinical Studies Groups and CTRad.

Delivery of SBRT in this setting is novel across the UK and an early assessment of patient recruitment and feasibility of delivery in a multi-centre setting is essential. Assuming feasibility of recruitment and deliverability of SBRT are confirmed, an efficacy signal will be sought after across the three tumour sites. Assessing efficacy overall rather than in individual sites at this stage will enable a positive signal to be identified more quickly and at present there is no strong biological rationale why SBRT would be effective for some tumour sites and not others.

If a positive signal is seen in the phase II then the intention is for CORE to expand to parallel phase III trials. Unless there are data to suggest that a phase III trial will not be feasible in a particular tumour type, separate phase III trials are planned for breast, NSCLC and prostate cancer patients. The design and primary endpoint for the phase III trial has not been fixed in advance; this will allow better estimates of treatment effect and the experience gained in the phase II part of the trial in terms of the deliverability of SBRT nationally to be taken into account in phase III. In addition, data collected during phase II on the secondary endpoints will be used to inform the design of the phase III and support power calculations and therefore, in any revised design, patients from the phase II part will not be included in the analysis of phase III endpoints. This approach will also provide an opportunity to refine the intervention technique prior to initiation of phase III on the basis of experience gained in phase II if required.

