11.1.2 Sample size

This phase II screening study has been designed with a primary endpoint of PFS, and relaxed one-sided $\alpha=0.20$ and $\beta=0.20$ (13). The control arm PFS is estimated based on the expected contribution of each primary tumour site to the overall final sample size. Based on observed recruitment in the first year this is estimated at 75% prostate, 14% breast and 11% lung. Assuming a median PFS of 5 months for NSCLC, 12 months for breast and 18 months for prostate patients (14-22), it is estimated that the median PFS in the control group after randomisation will be 16 months. The phase II SABR-COMET trial targets a hazard ratio (HR) for OS of 0.6 (23). For CORE, a more conservative effect size has been chosen reflecting clinical opinion of what would constitute a PFS signal worthy of a phase III OS trial. In order to detect a HR of 0.75 for improvement of PFS i.e. extending the median cohort PFS by 4 months in the experimental arm with 80% power, a total of 230 patients are required (138 events). Assuming a 5% rate of patients lost to follow up at the point of data analysis, a total of 242 patients will be required (121 per treatment group). Dependent on observed rates of accrual this total may increase to a maximum of 270 to allow for each cohort to achieve a minimum of 50 patients. The sample size calculations, made using the *artsurv* command in Stata version 13, assume 50% recruited in both years 1 and 2 and 12 months of additional follow up.

The decision rule to proceed to phase III will be based on a 3 outcome design. An overall result significant at the 10% level would support continuation to phase III; significance between 10% and 20% would require supportive evidence from secondary endpoints with a particular emphasis on local tumour control and FFWMD. If the significance is >20% then the study will not progress to phase III unless there is clear

heterogeneity of outcomes between the 3 tumour subgroups supporting a signal in selected tumour sites in which case consideration would be given to progressing to an extended phase 2 evaluation for that tumour site alone.

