11.2.5 Interim analyses and stopping rules

With the early assessment of feasibility there will be opportunities to stop the trial early should accumulating data justify this based on recruitment, treatment deliverability or toxicity.

Feasibility of recruitment: The IDMC and TSC will monitor recruitment rates and may recommend on trial closure if these are significantly less than expected and continuation of the trial is felt futile. Recruitment feasibility will be assessed by the number of open centres, patient acceptance rates and the number of patients randomised. For example, target recruitment is 20% year 1, 30% year 2 and 50% year 3, if actual recruitment is not at least half of what is targeted (i.e. at least 10% in year 1) then consideration would be given for closing the study due to it not being feasible to complete within a timely manner. If the acceptance rate amongst eligible patients falls below 50% this will trigger review of the recruitment process at sites by the Trial Management Group; if acceptance rates fall below 33% this will trigger referral to the TSC.

Deliverability of SBRT: At least 85% of patients randomised to SBRT + SOC are anticipated to receive their allocated SBRT treatment in the absence of new developing widespread disease and within the dosimetric constraints outlined in the SBRT protocol.

Safety: The IDMC will monitor safety with a formal review after 10, 34 and 51 patients have been treated with SBRT and followed up for 6 months. Consideration would be given to stopping the trial if the late grade 4/5 toxicity rate exceeds 5% in the experimental arm.

There are no early stopping rules for efficacy planned during the phase II component of this trial.

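### The recruitment endpoint in 11.2.2 contains no time or tumour type and divides by 206, which matches no sample size in the protocol, so it says little about feasibility once the target is met

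*Protocol*

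**What the plan says.** - **Endpoint.** Section 4.2 lists it as "Recruitment rate and proportion of patients receiving SBRT (if allocated) in the absence of new developing widespread disease". Section 11.2.2 defines it: "Recruitment rate is defined as the proportion of patients recruited to the trial. The denominator is the total number of patients required", and puts that number at 206. Neither place gives a time unit, a split by tumour type or a threshold.
- **Sample size.** Section 5.1 aims for 230 patients, with a ceiling of 270. Section 11.1.2 also gives 230 (138 events), raises it to 242 for 5% loss to follow-up, and repeats the ceiling of 270.
- **What the aim is for.** Section 3 makes feasibility of recruitment the first of three phase II aims: "If all three aims are achieved the trial will be amended to roll into parallel tumour-site specific phase III trials". Section 11.1.1 plans a phase III trial in each tumour type, with the proviso "Unless there are data to suggest that a phase III trial will not be feasible in a particular tumour type".
- **Monitoring.** Section 11.2.5 judges recruitment feasibility on centres open, acceptance and numbers randomised. By way of example it says "target recruitment is 20% year 1, 30% year 2 and 50% year 3", with closure considered below half of target. Acceptance below 50% prompts review by the Trial Management Group, and below 33% referral to the Trial Steering Committee.
- **Accrual behind the sample size.** The calculations in 11.1.2 "assume 50% recruited in both years 1 and 2 and 12 months of additional follow up".

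**The concern.** A recruitment rate should show how fast patients came in, and here from which tumour types, because phase III is to be run separately by type. The defined ratio has only two inputs: a count and a fixed number. Once the target is met, the answer depends only on where recruitment stopped. A trial that filled quickly with all three tumour types and one that filled slowly with almost none of two of them would report the same figure.

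The other two phase II aims have numbers attached: significance levels of 10% and 20% for activity (11.1.2) and an anticipated 85% for SBRT delivery (11.2.5). The recruitment aim has only this ratio as its endpoint, and the three-outcome rule in 11.1.2 contains no recruitment criterion. At stake is how much the end-of-phase-II report can say about whether breast and NSCLC phase III trials could recruit. The PFS comparison is not affected.

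**Working it through.** **1. Which number of patients is required?** Inputs from 11.1.2: HR 0.75, one-sided alpha 0.20, power 80%, 1:1 allocation. With (z_alpha + z_beta)² = (0.8416 + 0.8416)² = 2.833:
- Schoenfeld: 4 × 2.833 / (ln 0.75)² = 11.33 / 0.0828, giving 137 events.
- Freedman: 2.833 × (1.75 / 0.25)² = 2.833 × 49, giving 139 events.

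The stated 138 lies between the two and reproduces. A simple exponential model (medians 16 and 21.3 months, 24 months of uniform accrual, 12 months of follow-up) turns 137 to 138 events into about 236 to 238 patients, close to the stated 230. Loss inflation: 230 / 0.95 = 242.1, agreeing with 242. So 230 and 242 belong to the current design. The figure of 206 is not explained anywhere in the protocol.

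**2. The endpoint at each stopping point.** Endpoint = recruited / 206.

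| Recruited | / 206 | / 230 | / 242 |
|---|---|---|---|
| 206 | 100% | 89.6% | 85.1% |
| 230 | 111.7% | 100% | 95.0% |
| 242 | 117.5% | 105.2% | 100% |
| 270 | 131.1% | 117.4% | 111.6% |

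The stated denominator reaches 100% 24 patients short of 230. Correcting it removes that error, but the ratio is still at least 100% whenever the chosen target is met.

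**3. Time.** For 230 patients:
- over 2 years: 230 / 24 = 9.6 per month
- over 3 years: 230 / 36 = 6.4 per month
- over 6 years: 230 / 72 = 3.2 per month

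The endpoint is 111.7% in all three cases.

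**4. Tumour type.** Section 11.1.2 gives a mix of 75% prostate, 14% breast and 11% lung.
- 230 patients: 172.5 prostate, 32.2 breast, 25.3 NSCLC.
- 270 patients: 202.5 prostate, 37.8 breast, 29.7 NSCLC.

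At either total the endpoint is above 100%, while breast and NSCLC fall below the 50 per cohort that 11.1.2 names as the reason for going to 270. This assumes the mix stays as stated. Recruitment directed at the smaller cohorts would change the counts, but not the endpoint.

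**5. The two accrual plans.**

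| | Year 1 | Year 2 | Year 3 | Half of year-1 target |
|---|---|---|---|---|
| 11.2.5 | 20% | 30% | 50% | 10% |
| 11.1.2 | 50% | 50% | – | 25% |

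On 230 patients, the year-1 target is 46 under one plan and 115 under the other. Half of it is 23 or 57.5. After two years the first plan expects 50% of patients and the second 100%.

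**The case against.** A reader might infer that recruitment feasibility cannot fail as a gate to phase III. The documents do not support that.

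- Section 3 gates on the aim, not on this ratio, and 11.2.2 gives the ratio no pass mark.
- Section 11.2.5 says separately how feasibility is judged, with yearly targets and acceptance triggers that can be missed.
- A trial closed short of 206 would read below 100%. Saying that the ratio is always at least 100% on completion already assumes that recruitment succeeded.

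A reader might also infer that the protocol has no means of seeing that one tumour type is infeasible. That too goes further than the text. Section 5.1 ties any extension to accrual within each cohort, 11.1.2 names a minimum per cohort, and the screening log in 6.1 is kept partly for phase III planning. The proviso in 11.1.1 refers to data in general and not to the 11.2.2 ratio.

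Two more points carry some weight. The yearly targets are offered as an example, and missing them leads only to consideration of closure. Section 11.1.2 also already uses first-year recruitment, so the year-1 checkpoint had passed when this text was written, and the 10% against 25% difference now has little practical effect there.

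These points remove the stronger readings. They do not repair the endpoint: it still has the wrong denominator, no time and no tumour type, and no stated link to the criteria in 11.2.5. The contradiction between the accrual plans remains.

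**Conclusion.** The point holds in a limited form. The endpoint divides by a number that matches none of 230, 242 or 270, reaches 100% at 89.6% of 230, and reads 111.7% to 131.1% between 230 and 270 patients whatever the accrual time or tumour mix. In a trial that meets its target it does not inform the recruitment aim or the planning of phase III by tumour type. The criteria that could inform them stand in 11.2.5, unconnected to the endpoint, and rest on an accrual plan that contradicts 11.1.2.

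The ratios are arithmetic on the protocol's figures. The cohort counts assume the stated mix continues. The finding concerns a secondary endpoint and how it supports a stated aim; it does not bear on the type I error or power of the PFS comparison. It is worth correcting because the remedy is cheap.

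**What to change.** 1. In 11.2.2 replace 206 with the current target, stating whether that is 230 or 242.
2. Define the endpoint as patients randomised within the planned recruitment period divided by the number planned for that period, reported overall.
3. Beside it, give counts and monthly accrual by tumour type as description only, and the acceptance rate among eligible patients from the screening log. A pass/fail threshold for each tumour type is not proposed: the protocol has no tumour-type targets by period, and such thresholds would be a debatable design choice on small cohorts.
4. State that the feasibility aim in section 3 is judged with reference to the criteria in 11.2.5.
5. Use one accrual plan in 11.1.2 and 11.2.5, so that half of target has one meaning. If the plan in 11.1.2 changes, rerun the sample size calculation on it.

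The cost is mainly wording. Primary site is recorded at randomisation (section 7) and screening outcomes are logged (6.1), so no new data are needed. The downside is that the feasibility figure may look less favourable, and the breast and NSCLC figures will rest on small numbers, about 32 and 25 of 230.

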5 PATIENT SELECTION & ELIGIBILITY

5.1 Number of participants

The aim is to recruit 230 participants; 115 to SOC and 115 to SBRT + SOC. To ensure maximum feasibility information is obtained for each cohort, recruitment beyond 230 is permissible, to a maximum of 270. The decision to continue recruitment will be dependent on observed rates of accrual within each cohort and existing timelines for recruitment. Any decision to continue past 230 will be agreed in advance with the Trial Steering Committee.

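### The recruitment-rate endpoint divides by 206, a total found nowhere else in the protocol; the 230 target omits the protocol's own 5% loss allowance; and 270 is very unlikely to give 50 per cohort at the stated mix.

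*Protocol*

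**What the plan says.** **Totals.** The protocol gives three different totals.

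- Synopsis and section 5.1: the target is 230. Section 5.1 says "The aim is to recruit 230 participants; 115 to SOC and 115 to SBRT + SOC". Going beyond 230, up to 270, is allowed with advance agreement of the Trial Steering Committee, depending on accrual within each cohort and on timelines.
- Section 11.1.2: 230 patients (138 events) are needed before losses and, after allowing for 5% lost to follow-up, "a total of 242 patients will be required (121 per treatment group").
- Section 11.2.2, defining the recruitment-rate endpoint: "The denominator is the total number of patients required (i.e. 206 patients").

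**Cohorts.** Section 11.1.2 gives the purpose of the ceiling: "this total may increase to a maximum of 270 to allow for each cohort to achieve a minimum of 50 patients". The same paragraph gives the case mix: "Based on observed recruitment in the first year this is estimated at 75% prostate, 14% breast and 11% lung".

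**Accrual.** The sample-size calculations in section 11.1.2 "assume 50% recruited in both years 1 and 2 and 12 months of additional follow up". Section 11.2.5 gives, as an example, "target recruitment is 20% year 1, 30% year 2 and 50% year 3".

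**The concern.** An endpoint defined as a percentage of the required number needs the number that the trial actually requires. With 206 the percentage is too favourable at every level of recruitment, and it reaches 100% while the trial is still short of either 230 or 242.

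The 230/242 conflict is of a different kind. Section 11.1.2 explains how the two figures relate, but the synopsis and section 5.1 take the smaller one as the target. Patients 231 to 242 are thus required in one section and an optional extension in another.

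The ceiling of 270 is justified by a cohort size that the mix quoted in the same paragraph does not produce. This matters because section 5.1 gives per-cohort feasibility information as the reason for extending, and section 11.1.1 plans separate phase III trials by tumour type.

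**Working it through.** **Inputs** (section 11.1.2 unless noted): one-sided alpha 0.20, beta 0.20, hazard ratio 0.75, 1:1 allocation (section 11.1.3), control median 16 months, even accrual over 24 months plus 12 months of follow-up, 5% loss, mix 75/14/11. Exponential PFS is my assumption.

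**1. Reproducing the protocol's own figures**

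- Events (Schoenfeld): 4(z₀.₈ + z₀.₈)² / (ln 0.75)² = 4(0.8416 + 0.8416)² / 0.2877² = 136.9, so 137. The Freedman formula gives 139. The stated 138 lies between them.
- Event probability: with medians of 16 and 16/0.75 = 21.3 months, it is 0.630 in the control arm and 0.530 in the experimental arm, mean 0.580. Then 137/0.580 = 236 patients, within 3% of the stated 230.
- Loss: 230/0.95 = 242.1, so 242.

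So 138, 230 and 242 follow from the stated inputs to a fair approximation. 206 does not: 206 × 0.580 = 119.5 events, about 77% power.

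**2. What the denominator of 206 does**

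| Recruited | Divided by 206 | Divided by 230 | Divided by 242 |
|---|---|---|---|
| 206 | 100% | 89.6% | 85.1% |
| 230 | 111.7% | 100% | 95.0% |
| 242 | 117.5% | 105.2% | 100% |

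**3. Recruiting only 230 with 5% lost**

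Evaluable patients: 230 × 0.95 = 218.5. Power = Φ(√d × 0.2877/2 − 0.8416), where d is the number of events. Lost patients are taken to contribute no events, which slightly overstates the cost.

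| Basis for events | Events, 230 with no loss | Power | Events, 218.5 | Power |
|---|---|---|---|---|
| Protocol's ratio, 138/230 = 0.60 | 138 | 80.2% | 131.1 | 79.0% |
| Re-derived probability, 0.580 | 133.4 | 79.4% | 126.7 | 78.2% |

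Leaving out the allowance costs about 1.2 percentage points on either basis. The rest of the gap between 78.2% and 80% comes from my event probability being a little lower than the protocol's.

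**4. Cohorts at the stated mix**

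| Total | Prostate (75%) | Breast (14%) | NSCLC (11%) |
|---|---|---|---|
| 230 | 172.5 | 32.2 | 25.3 |
| 242 | 181.5 | 33.9 | 26.6 |
| 270 | 202.5 | 37.8 | 29.7 |

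Reaching 50 at an unchanged mix needs 50/0.14 = 357.1 (358 patients) for breast and 50/0.11 = 454.5 (455) for NSCLC. With 270 patients, the binomial chance of at least 50 is about 0.023 for breast and 0.0002 for NSCLC.

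If prostate entry stopped when the total reached 230, the expected requirement would be 172.5 + 50 + 50 = 272.5, which is 2.5 above the ceiling. The three cohorts fit within 270 when prostate is at most 270 − 100 = 170. At a true share of 75%, the chance of 170 or fewer prostate patients among 230 is about 38%.

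**5. Accrual profiles**

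Section 11.1.2 has half of the patients entering in year 1; the example in section 11.2.5 has 20%. Half of the year-1 target is 25% on the first profile (about 60 of 242) and 10% on the second (about 24 of 242). With 20/30/50 over 36 months plus 12 months of follow-up, the mean event probability is 0.603, so 230 patients give about 139 events against 133 under 50/50. The mismatch does not lower power.

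**The case against.** **Consequence of 206.** Section 3 makes feasibility of recruitment one of three aims to be achieved before phase III, so a reader might infer that an inflated percentage could carry the trial forward. The documents do not support that. Section 11.2.5 judges feasibility by open centres, acceptance rates and numbers randomised, with triggers at 50% and 33% acceptance. The decision rule in section 11.1.2 rests on PFS significance. No section makes 100% of 206 a criterion, and a reported rate above 100% would show itself. A reader might also suppose that 206 is left over from an earlier design; the protocol does not say so. This part of the objection stands in full, but 206 is still wrong in an endpoint definition.

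**230 and 242.** Section 11.1.2 relates the two, section 5.1 lets recruitment go past 230, and the power lost is slight in a screening trial with one-sided alpha of 0.20. That is right about size. It does not settle which figure is the target.

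**The ceiling of 270.** A reader might infer that 270 can never give 50 per cohort, even if prostate entry closed at 230. That is too strong: the shortfall is 2.5 patients on a rounded, estimated share, and there is about a 38% chance that it would not arise. Section 5.1 also ties the extension to accrual within each cohort. What remains is that no limit on prostate entry is stated, and that at an unchanged mix the minimum is very unlikely to be met.

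**Accrual.** The 20/30/50 profile is introduced as an example, closure would only be considered, and first-year recruitment had already been observed when section 11.1.2 was written. The mismatch is a matter of consistency only.

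**Conclusion.** The denominator of 206 is a plain error. It contradicts the synopsis and sections 5.1 and 11.1.2, does not follow from the stated inputs, and inflates the reported recruitment rate by a factor of 1.12 (against 230) or 1.17 (against 242). The effect is on a reported secondary endpoint, not on the phase III decision.

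The synopsis and section 5.1 target the figure before losses. At 5% loss this gives about 127 to 131 events and 78% to 79% power instead of 80%, assuming exponential PFS and no events from lost patients.

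The 50-per-cohort purpose of the ceiling is not met in expectation: about 38 breast and 30 NSCLC patients at 270. This assumes that the first-year mix persists, since no rule in the protocol would change it.

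The accrual mismatch is minor.

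**What to change.** 1. Delete 206 and set the denominator in section 11.2.2 to the single required total used throughout. Either take 242 (121 per group) into the synopsis and section 5.1, or keep 230 everywhere and restate the power as about 78% to 79% after 5% loss. Either choice is sound.
2. In section 11.1.2, replace the 50-per-cohort justification for 270 with what that total is expected to deliver at the observed mix, about 38 breast and 30 NSCLC patients.
3. Reconcile the accrual profiles in sections 11.1.2 and 11.2.5, or say why they differ.

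All three are changes of wording. The cost is a less favourable recruitment percentage and a more modest cohort statement; choosing 242 also means committing to 12 more patients than the present target.

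No prostate cap is needed. A cap at 170 would not be a change of wording only: it would move the mix at 270 to about 63/18.5/18.5 and the weighted control median from 15.73 months (0.75 × 18 + 0.14 × 12 + 0.11 × 5, which the protocol rounds to 16) to about 14.5 (170/270 × 18 + 50/270 × 12 + 50/270 × 5), so the sample-size input would have to be revisited.
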